Exclusion Criteria: Individuals who 1) have cognitive impairment preventing completion of study assessment procedures, 2) meet current DSM-5 criteria for alcohol/substance use disorder, 3) meet criteria for lifetime history of opioid use disorder, 4) have taken stimulants, benzodiazepines, TCA, venlafaxine or duloxetine in the past seven days, 5) have a history of clinically significant cardiac arrhythmias or vasospastic disease, or an abnormal and clinically-significant ECG, 6) have history/current evidence of significant medical/ psychiatric illness that elevates risk for experiencing an adverse event (including current suicidal ideation), 7) have a known allergy to the study medications, or 8) are pregnant or breastfeeding. Additional exclusion criteria due to their effects on pain responses include 10) current peripheral neuropathy, 11) presence of Raynaud's phenomenon, 12) active vasculitis or severe peripheral vascular disease, 13) current infection, 14) confirmed diagnosis of periodic limb movement disorder or restless legs syndrome, 15) systemic inflammatory or autoimmune disorders such as rheumatoid arthritis, lupus, etc., 16) seizure disorder, or 17) have a chronic pain condition that produces pain greater than their KOA.

6. Drugs/ Substances/ Devices

- The rationale for choosing the drug and dose or for choosing the device to be used.

We have strategically selected hydromorphone and dronabinol for this study, both drugs will be encapsulated by the BPRU pharmacy to ensure double-blind administration, and placebo will consist of lactose or another benign weight-matched filler. See Table 1 above for drug dosing details.

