a. Hydromorphone: Administration of any drug involves some risk because it is not always possible to predict individual response to drugs. The most likely risk in this study is that subjects will experience side-effects of the drugs that may be unpleasant. Common side effects of hydromorphone are light-headedness, dizziness, sedation, nausea, vomiting, sweating, flushing, dysphoria, euphoria, dry mouth, and pruritus. Less frequently observed side effects are weakness, headache, agitation, tremor, uncoordinated muscle movements, alterations of mood (nervousness, apprehension, depression, floating feelings, dreams), muscle rigidity, paresthesia, muscle tremor, blurred vision, nystagmus, diplopia and miosis, transient hallucinations and disorientation, visual disturbances, insomnia, increased intracranial pressure, flushing of the face, chills, tachycardia, bradycardia, palpitation, faintness, syncope, hypotension, hypertension, bronchospasm and laryngospasm, constipation, biliary tract spasm, ileus, anorexia, diarrhea, cramps, taste alteration, urinary retention or hesitancy, antidiuretic effects, urticaria, other skin rashes and diaphoresis. Side effects of hydromorphone are generally temporary, dissipate within several hours, and are dose-dependent. Thus, participants may only experience side-effects occasionally during the research study. Serious potential adverse effects of hydromorphone administration that are possible but extremely unlikely to be encountered in this study are respiratory depression and loss of consciousness. The FDA has identified the following conditions as increasing the risk for respiratory depression or other serious side effects following hydromorphone administration: patients with status asthmaticus; chronic obstructive pulmonary disease; reduced respiratory function; high blood pressure; impairment of hepatic, pulmonary or renal functions; myxedema or hyperthyroidism; adrenocortical insufficiency; gall bladder disease; acute alcoholism; history of convulsive disorders; history of head injury; currently taking sedatives, hypnotics or phenothiazines; and sulfite allergy. Mean exposure to hydromorphone is also increased 4-fold among patients with hepatic impairment and 3-fold among patients with renal impairment. The BPRU has extensive experience administering hydromorphone to opioid naïve individuals and employs well-established and rigorous eligibility criteria to ensure that individuals who may be more prone to experiencing opioid-induced side effects will not be admitted into the study.

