
The most serious potential adverse event following hydromorphone administration is opioid agonist overdose, which is characterized by respiratory depression, somnolence progressing to stupor or coma, skeletal muscle flaccidity, cold and clammy skin, constricted pupils, and sometimes bradycardia and hypotension. In serious overdosage, particularly following intravenous injection, apnea, circulatory collapse, cardiac arrest, and death may occur. We believe the risk of overdose in this study to be low for the following reasons: we have extensive experience in the administration of hydromorphone, we have chosen a dose that has been demonstrated to be safe and tolerable in similarly opioid inexperienced participant populations, we will exclude any individual who has a medical condition that may increase the risk for respiratory depression and/or other adverse events, all medication doses will be administered by a trained research nurse, and participants will be closely monitored by trained staff who will have access to

the opioid antagonist naloxone to reverse the opioid agonist effects. Additional protections against the risk of hydromorphone side effects, including overdose, are discussed in the Protection Against Risks section. Hydromorphone has no known interactions with dronabinol.

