a. Protection Against Hydromorphone Risks: We have extensive experience in the administration of hydromorphone and other opioid agonists in controlled laboratory settings and therefore anticipate few problems. Any individual who may be prone to the risks associated with hydromorphone will be excluded from participating. Although research staff and participants will be blinded to the exact medication provided, both groups will be informed of the potential side effects and risks associated with the study drug administration. Participants will be free to discontinue study participation at any time without consequence. The dose of hydromorphone that is being administered is consistent with clinical care, and is a medium level dose for the treatment of pain. Hydromorphone will always be administered along with placebo in the first session, which will provide a valuable opportunity to exclude from further participation any participant who experiences untoward effects (e.g., nausea, vomiting) resulting from that dose of hydromorphone. Great care has been taken in selecting the appropriate drug doses to ensure hydromorphone is well-tolerated and safe for our participants and participants will also be able to discontinue study participation at any time. The most serious risk associated with hydromorphone administration is respiratory depression. We believe this risk is minimal in this study for several reasons. First, we are administering a mid-level dose and have

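### Section 8 promises to exclude anyone prone to hydromorphone's risks, yet no Section 5 criterion names non-benzodiazepine sedatives or hypnotics, or phenothiazines, which Section 8 lists among those risks

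*Combined protocol and SAP*

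**What the plan says.** **The risk list.** Section 8.a (item a, Hydromorphone) lists conditions that raise the risk of respiratory depression or other serious side effects after hydromorphone. The list ends with people "currently taking sedatives, hypnotics or phenothiazines; and sulfite allergy".

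**The promise.** Section 8 says three times that people at raised risk are kept out.
- Section 8.a, on eligibility criteria: "individuals who may be more prone to experiencing opioid-induced side effects will not be admitted into the study".
- Section 8.a, among the reasons for judging overdose risk low: "we will exclude any individual who has a medical condition that may increase the risk for respiratory depression and/or other adverse events".
- Section 8.b (item a, Protection Against Hydromorphone Risks), without qualification: "Any individual who may be prone to the risks associated with hydromorphone will be excluded from participating".

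**The criteria.** In Section 5, exclusion 4 removes those who "have taken stimulants, benzodiazepines, TCA, venlafaxine or duloxetine in the past seven days". Exclusion 6 removes people with significant medical or psychiatric illness that raises adverse-event risk. Inclusion 6 requires medical eligibility for the study drugs. Section 4.a (Screening) bases that eligibility on an ECG, blood tests (hepatic, hematologic and chemistry), a history and physical, and a knee x-ray, all before the first dose. Section 4.g adds that participants are not asked to give up their routine medicines.

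**The concern.** The protocol defines a group at raised risk by the drugs they take and says that such people are excluded. The rule that screening staff apply to drugs covers only part of that group. A screener who follows Section 5 as written could admit someone whom Section 8.b says is excluded on safety grounds.

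Two things are at stake. An ethics board reading Section 8 would believe that a defined exclusion exists when it does not. And a participant already taking a sedating drug could be given hydromorphone, and in a later session hydromorphone with dronabinol, for which Section 8.a (item b) lists somnolence as an adverse effect.

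**Working it through.** No arithmetic applies, because no figure is in dispute. The check takes each drug group in the Section 8.a risk list and asks which stated criterion would stop a person taking it.

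**Step 1. Match the risk list to exclusion 4.** Exclusion 4 has five entries: stimulants, benzodiazepines, TCA, venlafaxine and duloxetine.

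| Drug group in the Section 8.a list | Named in exclusion 4? |
|---|---|
| Sedatives | Benzodiazepines only |
| Hypnotics | Benzodiazepines only |
| Phenothiazines | No |

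**Step 2. Look for another criterion that closes the gap.**
- Inclusion 4 concerns recent opioid use.
- Inclusion 5 is a urine test for illicit drugs and pregnancy. It is not a check on prescribed medicines.
- Inclusion 7 concerns a stable dose of NSAIDs or acetaminophen.
- Exclusion 2 concerns alcohol or substance use disorder. Ordinary prescribed use is not a disorder.
- Exclusion 6 concerns illness. A concomitant drug is not an illness, although the reason for taking it might be.
- Exclusion 7 concerns allergy to the study drugs.
- Inclusion 6, medical eligibility, is general. The Section 4.a work-up behind it includes a history, so a study physician may learn of such drugs. No sentence says that taking them makes a person ineligible.

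**Step 3. Ask whether the drug would be stopped anyway.** Section 4.g says that routine medicines continue.

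**Result.** For non-benzodiazepine sedatives and hypnotics, and for phenothiazines, no named criterion applies. The only route to exclusion is a physician's judgement under inclusion 6. That is a weaker protection than the unconditional statement in Section 8.b.

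**The case against.** The strongest reply is that Section 5 must be read as a whole. Inclusion 6 is open-ended and specific to the study drugs, and Section 4.a gives it real content. A physician taking a history could be expected to notice a hypnotic or a phenothiazine. The psychiatric screening in Section 8.b (item b) may also remove some phenothiazine users, though that is an inference. This reply narrows the gap. It does not close it, because the text leaves to judgement what Section 8.b presents as settled, and two physicians could decide differently.

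A second reply is that exclusion is one safeguard among several. Section 8.a also relies on experience with the drug, dose choice, administration by a nurse, close monitoring and access to naloxone. Section 8.b gives hydromorphone with placebo in the first session, so that anyone with untoward effects can be withdrawn before the combination. It also sets respiratory-rate and oxygen-saturation steps, and vital signs every 15 minutes for the first 2 hours. This stands: a reader should not infer that the whole safety case rests on the missing criterion. But these measures act after enrolment and do not make the statement about exclusion correct.

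A reader might extend the point to organ impairment, since the risk list includes "impairment of hepatic, pulmonary or renal functions" and Section 5 gives no numerical limit. The documents do not support that extension. The promise "we will exclude any individual who has a medical condition that may increase the risk for respiratory depression and/or other adverse events" is nearly mirrored by exclusion 6, and the screening work-up includes hepatic and chemistry bloods and a physical. A missing cut-off there is missing detail within a criterion that exists.

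**Conclusion.** The inconsistency is real and narrow. It concerns three drug groups in the protocol's own risk list: sedatives and hypnotics other than benzodiazepines, and phenothiazines. For these, the exclusion stated in Section 8.b has no named counterpart in Section 5, and only the general eligibility judgement stands in its place.

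Its size in participants cannot be given, because the documents contain no figure for use of these drugs among candidates. The conclusion rests on reading exclusion 6 as covering illness only, as it is worded, and on there being no separate screening document that lists further drugs.

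A reader might also take the statement "Mean exposure to hydromorphone is also increased 4-fold among patients with hepatic impairment and 3-fold among patients with renal impairment" and convert it into equivalent doses to size the problem. That would need an assumption of dose-proportional exposure, the documents give no severity of impairment for those ratios, and the ratios have no bearing on concomitant drugs. They are not evidence for this point.

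The correction should be made because a screening rule, applied as written, can admit people whom the protocol says are kept out for safety.

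**What to change.** Reconcile Section 5 and Section 4.g with the hydromorphone text in Sections 8.a and 8.b. There are two ways to do so.

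1. The study medical team decides, for each concomitant-drug factor in the Section 8.a list, whether it excludes a person. The same list then appears in exclusion 4 and in the screening checklist.
2. The unconditional statement in Section 8.b is narrowed to what Section 5 enforces, saying openly that other sedating drugs are left to the physician's judgement under inclusion 6.

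Which drugs should exclude is a clinical decision for the medical team, and this review takes no position on it. The cost is a protocol text amendment and a checklist update. The first option may add a few screen failures. Neither option changes the design or the analysis.

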i. *Hydromorphone (Dilaudid)* is a potent mu-opioid agonist that we have extensive experience administering in controlled laboratory settings. Hydromorphone is not subject to differences in CYP metabolic enzymes so will not require us to screen out individuals with recent exposure to CYP inhibitors/inducers, or to analyze/ statistically control for CYP metabolic profiles. The two (2 and 4 mg) oral doses of hydromorphone are commercially-available and regularly used for analgesia, which increases the clinical relevance of these results. We expect both doses of hydromorphone to exert a moderate analgesic effect on pain, which is an important feature because too strong a dose could overwhelm the cannabinoid effect and prevent us from effectively evaluating the study aims. Including both a low and moderate dose will provide an elegant assessment of whether a cannabinoid will produce an additive, synergistic, or no effect on the analgesic profile of hydromorphone.

ii. *Dronabinol (Marinol)* has been strategically chosen for this study because it is a widely-used, commercially-available Schedule II cannabinoid medication that is currently indicated for nausea and vomiting, and anorexia in AIDS patients, **but which could be prescribed off-label for the adjunctive treatment of clinical pain.** Dronabinol is a synthetic delta-9-tetrahydrocannabinol (THC) product (the primary psychoactive compound in cannabis sativa (marijuana)), and thus has generality with other THC compounds (such as smoked or edible marijuana products). When administered orally (as proposed here),

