Hydromorphone: Hydromorphone hydrochloride is a pure mu opioid agonist that can be administered in oral, rectal, intramuscular (IM) or intravenous (IV) formulations for the indication of acute and/or chronic pain. We have chosen to administer hydromorphone because we have extensive experience administering hydromorphone in all formulations^{96; 109-117}, and know that it will produce reliable and consistent results that will aid interpretation of outcomes. Hydromorphone was also selected as the exemplar opioid for this study because it is not subject to differences in CYP metabolic enzymes and therefore will not require us to screen out individuals with recent exposure to CYP inhibiting or inducing medications, or to analyze and statistically control for CYP metabolic profiles in individual subjects. There is also no apparent effect of gender on the pharmacokinetics of hydromorphone. We have selected a low and mid-level dose because they are within the range of doses approved by the FDA. They are also sensitive to the QST tests we have proposed, and we therefore believe both will provide an ideal opportunity to evaluate whether the curve of hydromorphone is shifted as a function of dronabinol administration.

Dronabinol: Dronabinol is a schedule II drug that is being administered at 10 mg, which is consistent with the range approved by the FDA for therapeutic use in patients with chemotherapy-induced nausea and vomiting, and loss of appetite in patients with advanced HIV (AIDS). Dronabinol is also used off label for the treatment of Gilles de la Tourett's syndrome, general loss of appetite (related to cancer), spasticity from Multiple Sclerosis, treatment refractory and postoperative nausea and vomiting, and treatment refractory pruritus. When administered orally (as proposed here), dronabinol reaches peak concentrations in 2-4 hours and is 10-20% bioavailable. It is subject to extensive first-pass metabolism and is excreted in fecal (35-50%) and renal (10-15%) waste, with an elimination half-life of 19-36 hours.

We have selected oral dronabinol because it is FDA approved for pain conditions and more likely than nabilone to be prescribed in practice due to cost. We believe this approach will yield data that can be instantly utilized by pain treatment specialists, which increases the generalizability of our study approach.

c. Justification and safety information if non-FDA approved drugs without an IND will be administered.

N/A

7. Study Statistics

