a. Primary outcome variable:

Aim 1: Evaluate the magnitude and duration of cannabinoid/opioid combination to reduce clinical pain (Hyp1) and central sensitization (Hyp2). Hyp1 (pain VAS) and Hyp 2 (CS) will be analyzed using repeated 2-factor (Drug x Time) models that examine linear and quadratic effects as well as duration and magnitude, and direct and interaction effects. If large variation exists across subjects at baseline, then raw data will be transformed to change-from-baseline and analyzed in drug condition by time models. A secondary outcome will be peak change from baseline, analyzed as a function of Drug (1-factor model).

- Aim 2: Evaluate the degree to which physical functioning is altered by the cannabinoid/opioid combination.** Hyp3 will be assessed using the TUG and 6MWT. Time to complete the TUG task will be the primary outcome and will be evaluated using 2-factor (Drug x Time: Pre to Peak) models.
- Aim 3: Conduct a direct comparison of the subjective, physiological, abuse liability, and cognitive effects of the cannabinoid, opioid, and combination.** Hyp4 (adverse events) will be assessed by summing the mean number of related mild, moderate, and severe adverse events (separately) and using 1 factor models to assess a main effect of Drug. Hyp5 (abuse liability) will be assessed using the Drug vs. Money questionnaire and changes in VAS ratings using 2-factor models (Drug x Time). Hyp6 will evaluate changes in neurocognitive performance, including study session number as a covariate to control for practice effects, using 2-factor (Drug x Time) analyses. Secondary outcomes for this hypothesis will be analysis of peak change from baseline for the cognitive outcomes, analyzed using 1-factor (Drug) ANOVAs to evaluate a main effect of drug.

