- Aim 4: Evaluate the pharmacokinetic (pK) and pharmacodynamic (pD) profile of the cannabinoid, opioid, and the combination in OA patients.** Hyp 7 (pK) will be assessed by evaluating Cmax (maximum concentration) and Tmax (time to maximum concentration) as a function of Drug condition using 1-factor models. We will also examine linear and quadratic effects to evaluate the time course of concentration. Linear and quadratic effects will be modeled for Hyp8 (pD) and analyzed by evaluating VAS and physiological ratings, transformed to change from baseline, evaluating area under the curve and peak change from baseline to identify main effects of the Drug condition. We will then conduct multivariate regression analyses to evaluate the degree to which the Cmax and Tmax correlate with pharmacodynamic outcomes, including abuse liability ratings, VAS ratings of drug effects, and cognitive testing outcomes.

Statistical analyses will be conducted separately by Phase and use multilevel analyses with an autoregressive (AR1) or compound symmetry (CS) covariance structures (as appropriate for the data set) using SAS PROC MIXED¹³⁷. Interpretation of drug condition main effects and interactions will rely on Tukey post-hoc tests. Statistical significance will be set at $p < 0.05$.

Expected Outcomes: We expect that dronabinol will enhance hydromorphone-induced analgesia to both clinical and laboratory-evoked pain. Our comprehensive battery of rigorous, testing procedures provides an opportunity to test effects on multiple mechanisms of experimentally-induced pain. We also expect improvement in physical functioning under combined dosing, and that the addition of the cannabinoid will not significantly increase the overall abuse liability or adverse event profile. We do suspect the cannabinoid may have cognitive effects (though the degree to which this may happen is not clear).

b. Secondary outcome variables.

Demographic and drug use characteristics that are hypothesized a priori to be associated with outcomes (e.g., Body Mass Index) will be compared across sex groups and significant differences will be included as covariates in the subsequent analyses. All analyses will be repeated and sex (male/female) will be added as a factor to the analyses.

c. Statistical plan including sample size justification and interim data analysis.

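### The dose rationale promises to separate additive from synergistic effects, but no planned analysis tests departure from additivity

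*Combined protocol and SAP*

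**What the plan says.** The promise is in the rationale for drug and dose. In section 6, the hydromorphone paragraph says that having two doses will give an "assessment of whether a cannabinoid will produce an additive, synergistic, or no effect on the analgesic profile of hydromorphone". Section 6b repeats the idea, saying that the two doses give an opportunity to "evaluate whether the curve of hydromorphone is shifted as a function of dronabinol administration".

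The analysis is in section 7a. Pain and central sensitization (Aim 1) are analysed with "repeated 2-factor (Drug x Time) models that examine linear and quadratic effects as well as duration and magnitude, and direct and interaction effects". Peak change from baseline is a secondary outcome in a one-factor Drug model, and area under the curve appears under Aim 4. For all aims, "Interpretation of drug condition main effects and interactions will rely on Tukey post-hoc tests" and "Statistical analyses will be conducted separately by Phase".

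The hypotheses for Aims 1 and 2 (section 2) compare the combination with each drug alone and with placebo. Tables 1a and 1b show that each Phase contains all four cells: placebo, hydromorphone, dronabinol and both. Hydromorphone alone is always given in session 1, and only the other three conditions are in random order (section 4a; repeated in section 8b).

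**The concern.** Two drugs are additive on an outcome when the combined effect equals the sum of the separate effects, each measured against placebo. Deciding this needs a comparison that uses all four condition means. The plan has no hydromorphone-by-dronabinol term, no contrast of the combination with the sum of the single-drug effects, no definition of additive or synergistic, and no comparison across the two hydromorphone doses.

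The risk lies in interpretation. A result in which the combination beats either drug alone could be reported as synergy, although it is just as expected under simple additivity and can occur under sub-additivity. With nothing prespecified, any statement about additivity would rest on an analysis chosen after the data were seen.

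**Working it through.** **Inputs.** Four conditions per Phase (Tables 1a, 1b); alpha 0.05 (section 7a), taken as two-sided; power 0.8 (section 7c). The documents give no SD, within-person correlation or numeric effect size, so I assume an outcome SD of 1 and a common correlation of 0.5. Number per Phase: section 4a gives 100 split equally, so 50. Section 7c gives 64 completers (32 per sex), which is 32 per Phase if 64 is the total. If 64 is per Phase the total is 128, more than the 100 planned; I keep 64 as the upper end of the range.

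**The plan's own figure.** Section 7c says that 10 to 15 people suffice for large effects. This reproduces. A paired t-test at d = 0.8 needs 15 (two-sided) or 12 (one-sided). A four-condition repeated-measures F test at f = 0.4 needs 10 at correlation 0.5 and 14 at 0.3. Section 7c claims power for direct effects of condition, not for additivity.

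**The missing contrast.** Write P, H, D, C for the means under placebo, hydromorphone, dronabinol and combination. Additivity is C - P = (H - P) + (D - P), that is

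I = (C - H) - (D - P) = 0.

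None of the six pairwise differences equals I.

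**Precision.** Var(pairwise difference) = 2 x SD² x (1 - rho) = 2 x 1 x 0.5 = 1. Var(I) = 4 x SD² x (1 - rho) = 4 x 1 x 0.5 = 2. The ratio is 2 at any common correlation, so detectable sizes differ by √2.

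| Completers per Phase | Detectable at 80% power, pairwise | Detectable at 80% power, I |
|---|---|---|
| 32 | 0.51 | 0.51 x 1.414 = 0.72 |
| 50 | 0.40 | 0.40 x 1.414 = 0.57 |
| 64 | 0.36 | 0.36 x 1.414 = 0.50 |

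Sizes are in SDs of a paired difference; products use unrounded values. Completers needed for I = 0.8, 0.5 and 0.2 are 27, 65 and 395, against 15, 34 and 199 for pairwise differences of the same size. For I = 0.5 outcome SDs the need runs from 90 to 40 as the correlation goes from 0.3 to 0.7.

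**Does winning every comparison discriminate?** I simulated 20,000 trials per cell, with Tukey adjustment on the pooled within-subject error. Entries are the percentage of trials in which the combination beats all three comparators.

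| Means (P, H, D, C) | I | n = 32 | n = 50 | n = 64 |
|---|---|---|---|---|
| Additive (0, 0.5, 0.5, 1.0) | 0 | 43 | 72 | 87 |
| Sub-additive (0, 0.7, 0.7, 1.2) | -0.20 | 42 | 73 | 87 |
| Synergistic (0, 0.25, 0.25, 0.75) | +0.25 | 42 | 72 | 86 |

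Separate simulations of the additive case at n = 32 gave 43% to 45%. A test of I rejects in about 5% of the additive trials, as it should. It rejects in 12%, 16% and 20% of the sub-additive trials and 16%, 24% and 29% of the synergistic ones. It asks the right question, but departures of this size would usually be missed.

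**Session 1.** Let s be the mean shift in session 1 and m the average shift over sessions 2 to 4. With balanced order, C, D and P each carry m and H carries s. I = C - H - D + P is therefore shifted by m - s - m + m = m - s. No other condition occurs in session 1, so a session covariate cannot remove this.

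**The case against.** The strongest reply is that the study is not built on this claim. Aim 1 asks whether the combination exceeds each drug alone and placebo, and Tukey comparisons answer that directly. The additive/synergistic statement is one sentence of dose rationale, not an objective, hypothesis or outcome. This stands. A reader might infer that the main hypotheses are untestable, or that the design cannot address additivity; the documents support neither. The hypotheses are matched to their tests, and the 2x2 is complete in each Phase.

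A second reply is that section 7a mentions interaction effects. The two factors named there are Drug and Time, so that interaction asks whether time courses differ across conditions. Nor does the plan consist of Tukey tests alone: it also has linear and quadratic time terms, peak change and area under the curve. None of these tests additivity.

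A third reply is that all six pairwise results together carry information. They do: at 64 completers, hydromorphone differs from placebo in about 91% of the additive trials and 27% of the synergistic ones. But a pattern of significant and non-significant results is not a test of I and has no stated error rate.

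Finally, the promise rests on two doses. Each dose is given to different people and analysed separately, so the contrast within a Phase meets only part of it.

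**Conclusion.** The mismatch between the dose rationale (sections 6 and 6b) and the analysis (section 7a) is real. It is confined to the additive/synergistic and curve-shift statements and does not impair Aim 1. That no pairwise difference equals I is algebra and needs no assumption. The win rates of about 43%, 72% and 87% depend on the assumed means, paired-difference SD of 1, equal correlations and 32 to 64 completers per Phase. The near-equality of the three scenarios holds at each size examined, for scenarios chosen so that the combination exceeds each single drug by the same 0.5. The point should be corrected in the plan; it is not a fatal flaw.

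**What to change.** In section 7a, within each Phase, prespecify (combination - hydromorphone) - (dronabinol - placebo) from the planned mixed model, on one named summary that is already planned, and report it with its 95% CI. Peak change from baseline is one candidate. If the two drugs peak at different times, effects that add at every time point need not add at the peak; an area summary avoids this. Base any use of additive, synergistic or sub-additive on this contrast and not on the Tukey comparisons.

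State its limits beside it:

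- Its variance is twice that of a pairwise difference. A non-significant result does not show additivity: under the assumptions above the 95% CI is about ±0.51, ±0.40 and ±0.35 at 32, 50 and 64 completers (t x √2 / √n).
- It tests additivity of effect on the chosen scale, not dose-additivity.
- Any session-1 effect enters it in full, because hydromorphone alone is always first.

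Soften the curve-shift statement in section 6b, or add a descriptive comparison of the contrast across the two doses. If the contrast is not adopted, withdraw the additive/synergistic claim in section 6.

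The cost is wording and one extra contrast, with no new conditions, visits or participants. The downside is an imprecise estimate and a more cautious claim.
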